7.2 Dose Modifications of Cholestyramine

Cholestyramine will be administered and dose modified per the discretion of the treating investigator in agreement with standard administration practices.

8.0 AGENT INFORMATION

8.1 Leflunomide

Leflunomide is an FDA approved agent for the treatment of rheumatoid arthritis. Please refer to the Package Insert for additional details not provided in this section.

8.1.1 Description and classification

The chemical name for leflunomide is N-(4'-trifluoromethylphenyl)-5-methylisoxazole-4-carboxamide. It has a molecular formula C₁₁H₁₁F₃N₂O, a molecular weight of 270.2. Leflunomide is a pyrimidine synthesis inhibitor.

8.1.2 Mode of action

Leflunomide is an isoxazole immunomodulatory agent which inhibits dihydroorotate dehydrogenase (an enzyme involved in *de novo* pyrimidine synthesis) and has antiproliferative activity. Several *in vivo* and *in vitro* experimental models have demonstrated an anti-inflammatory effect.

8.1.3 Toxicology

See [Section 6.1](#)

8.1.4 Pharmacology

Following oral administration, leflunomide is metabolized to an active metabolite teriflunomide (A77 1726) which is responsible for essentially all of its activity *in vivo*. Following oral administration, peak levels of the active metabolite occurred between 6 to 12 hours after dosing. Due to the very long half-life of teriflunomide (~2 weeks), a loading dose of 100 mg for 3 days was used in clinical studies to facilitate the rapid attainment of steady-state levels of teriflunomide. Without a loading dose, it is estimated that attainment of steady-state plasma concentrations would require nearly two months of dosing. Biliary recycling is a major contributor to the long elimination half-life of teriflunomide. The active metabolite of leflunomide is eliminated slowly from the plasma. Use of a drug elimination procedure (cholestyramine or activated charcoal) is used to reduce the drug concentration more rapidly after stopping leflunomide therapy.

8.1.5 Storage and stability

Leflunomide tablets should be stored at 25°C (77°F); excursions are permitted to 15–30°C (59–86°F). Protect from light.

8.1.6 Preparation

Leflunomide is commercially available for oral administration as tablets containing 10, 20, or 100 mg of active drug.

8.1.7 Agent administration

Leflunomide is administered orally. Participants will be given a study calendar to track all doses taken or missed. There will be an initial loading dose of 100 mg/day for the first 3 days of doses. Participants will then receive leflunomide at the assigned dose level. See [Section 5.3.1](#) for administration details.

8.1.8 Availability and supply

Tablets in 10 and 20 mg strengths are packaged in bottles of 30 pills per bottle. Leflunomide will be provided to patients by the study as an investigational agent. A commercial supply will be purchased and distributed as an investigational agent by the Investigational Drug Pharmacy at City of Hope.

8.2 Cholestyramine

Cholestyramine is not the study agent being evaluated for efficacy, but is required for the elimination of the study agent leflunomide. Cholestyramine is FDA approved for hypercholesterolemia. **Cholestyramine use is indicated in the leflunomide package insert to eliminate the leflunomide metabolite.**

8.2.1 Description

Cholestyramine is a strong anion exchange resin comprised of a quaternary ammonium group attached to an inert styrene-divinylbenzene copolymer. Cholestyramine removes bile acids from the body by forming insoluble complexes with bile acids in the intestine, which are then excreted in the feces.

8.2.2 Other names

Questran®, Questran Light, Cholybar, Olestyr

8.2.3 Mode of action

Cholestyramine resin adsorbs and combines with the bile acids in the intestine to form an insoluble complex which is excreted in the feces. This results in a partial removal of bile acids from the enterohepatic circulation by preventing their absorption.

8.2.4 Toxicology

See [Section 6.2](#).

8.2.5 Storage and stability

Store between 20°-25°C (68°-77°F). [See USP Controlled Room Temperature]. Excursions permitted to 15°-30°C (59°-86°F).

8.2.6 Agent administration

Cholestyramine should be administered orally after being prepared per package insert (powder diluted in fluid). See [Section 5.3.2](#) for study administration details.

8.2.7 Availability and supply

Cholestyramine will be provided to participants by the study. A commercial supply will be purchased and distributed by the pharmacy at City of Hope.

[figure not shown]
9.0 CORRELATIVE/ SPECIAL STUDIES

9.1 Central Pathology Review

A slide from a baseline skin biopsy of the participant taken in the preceding 6 months must be sent to City of Hope for diagnostic review.

9.2 Skin Biopsies

The diagram below diagram provides an overview for the skin biopsy samples.

Figure 9.1 Overview of collection and analysis for CD30+LYPD tissue samples

9.2.1 Collection details

A single skin lesion will be sampled from participants at baseline and subsequent timepoints.

Samples will be a ~1x1 cm punch biopsy for all timepoints

9.2.2 Timepoints of collection

Lesion samples will be taken at the following timepoints:

- Pre-dose Cycle 1 Day 1 (baseline samples may be collected anytime post-informed consent and prior to the Cycle 1 Day 1 dose)
- Cycle 2 Day 1, and Cycle 5 Day 1 if lesions are present
- At end of protocol therapy (13 or fewer cycles) if lesions are present.
- At disease progression

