3.1 Inclusion Criteria

Informed Consent

- ___ 1. Documented informed consent of the participant and/or legally authorized representative.
 - Assent, when appropriate, will be obtained per institutional guidelines

Age Criteria, Performance status

- ___ 2. Age: ≥ 18 years
- ___ 3. Patients must have a life expectancy of > 3 months
- ___ 4. ECOG ≤ 2

Nature of Illness and Illness Related Criteria

- ___ 5. Patients must have a diagnosis of cutaneous CD30+LYPD
- ___ 6. Patients must be relapsed or are refractory to at least 1 prior line of therapy
- ___ 7. At least 2 weeks from prior therapy to time of start of treatment. Prior therapy includes steroids (except prednisone or equivalent – up to 10 mg/day is allowed).

Clinical Laboratory and Organ Function Criteria (To be performed within 21 days prior to Day 1 of protocol therapy unless otherwise stated [see Section 10.0])

 ___ 8. ANC $\geq 1000/\text{mm}^3$ NOTE: Growth factor is not permitted within 14 days of ANC assessment unless cytopenia is secondary to disease involvement. 	ANC: 	Date:

 ___ 9. Platelets $\geq 50,000/\text{mm}^3$ NOTE: Platelet transfusions are not permitted within 14 days of platelet assessment unless cytopenia is secondary to disease involvement. 	Plts: 	Date:

 ___ 10. ___ 10. Total bilirubin $\leq 1.5 \times \text{ULN}$ (unless has Gilbert's disease) 	ULN: Bil: 	Date:

 ___ 11. AST $\leq 2.0 \times \text{ULN}$ 	ULN: AST: 	Date:

 ___ 12. ALT $\leq 2.0 \times \text{ULN}$ 	ULN: ALT: 	Date:

 ___ 13. Creatinine clearance of $\geq 30 \text{ mL/min}$ per 24 hour urine test or the Cockcroft-Gault formula or $\text{CrCl (mL/min)} = \frac{(140-\text{age}) \times \text{actual body weight (kg)}}{72 \times \text{serum creatinine (mg/dL)}} \times 0.85 \text{ for females}$ 
Or
 $\text{CrCl (mL/min)} = \frac{(140-\text{age}) \times \text{actual body weight (kg)}}{0.8136 \times \text{serum creatinine (umol/L)}} \times 0.85 \text{ for females}$ 	Serum Cr: Cr Clearance: 	Date:

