3.2 Exclusion Criteria

Prospective participants who meet any of the following criteria will not be eligible for admission into the study:

Concomitant medications

- ___ 1. Current or planned use of other investigational agents, or concurrent biological, chemotherapy, or radiation therapy during the study treatment period. (See inclusion criterion #7 for washout times).
- ___ 2. Current or planned growth factor or transfusion support. If growth factor or transfusion support is provided between screening and start of treatment, the participant will no longer be eligible.

Other illnesses or conditions

- ___ 3. Prior Allogeneic transplant.
- ___ 4. Acute active infection requiring systemic therapy within 2 weeks prior to enrollment.
- ___ 5. Known history of hepatitis B or hepatitis C infection
- ___ 6. Known HIV infection.
- ___ 7. History of allergic reactions attributed to compounds of similar chemical or biologic composition to leflunomide or cholestyramine.
- ___ 8. Non-hematologic malignancy within the past 3 years aside from the following exceptions:
 - adequately treated basal cell or squamous cell skin cancer
 - carcinoma in situ of the cervix
 - prostate cancer < Gleason Grade 6 with a stable PSA
 - successfully treated in situ carcinoma of the breast

___9. Clinically significant medical disease or condition that, in the investigator's opinion, may interfere with protocol adherence or the patient's ability to give informed consent.

___10. Pregnant women and women who are lactating. Leflunomide has potential for teratogenic or abortifacient effects. Because there is a potential risk for adverse events in nursing infants secondary to treatment of the mother with these agents, breastfeeding should be discontinued if the mother is enrolled on this study.

___11. Any other condition that would, in the Investigator's judgment, contraindicate the patient's participation in the clinical study due to safety concerns or compliance with clinical study procedures, e.g., infection/inflammation, intestinal obstruction, unable to swallow medication, social/ psychological issues, etc.

Noncompliance

___12. Prospective participants who, in the opinion of the investigator, may not be able to comply with all study procedures (including compliance issues related to feasibility/logistics).

Eligibility Confirmed* by (Choose as applicable):	Print Name	Signature	Date
 Site PI			
 Authorized study MD			

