5.9.2 Prohibited medications

- Exposure to any new immunosuppressive medication in the 4 weeks prior to enrollment.
- Patients may not be receiving any other parenteral investigational agents. Oral chemotherapeutic agents or biologics –for example ruxolitinib, rituxan, ibrutinib therapy (either past or current exposure) - is allowed.
- The use of medication that are CYP1A2 inducers and CYP2C8 inhibitors and vitamin K antagonists are prohibited.

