9.2.6 Single Cell RNA Sequencing

The samples at baseline and beginning of cycle 2 for each patient will be analyzed together to identify changes in both CD30 tumor cells and other immune cell populations. Cells with mitochondrial read rate > 10% and < 200 detectable genes are considered as low-quality and filtered out. Unwanted sources of variation will be regressed out of the data by constructing linear models to predict gene expression based on the number of UMIs per cell as well as the percentage of mitochondrial gene content. Normalized and scaled data will be clustered using the top significant principal components of the highly variable genes. The t-distributed stochastic neighbor embedding (t-SNE) algorithm will be used to visualize the resulting clusters. Cluster specific markers will be identified to generate heatmap and identify cell types in each cell cluster. T cell subtype markers, such as T reg, memory T cells, effector T cells, exhausted T cells etc. will be used to identify different T cell populations. Chromium's V(D)J-Loupe will be used for analysis of TCR clonotypes and for visualization. Over-represented TCR clone in each patient will be identified and considered as indication of malignant cells. Genes will be compared between malignant and non-malignant cells using Bioconductor package "Limma" on log transformed and normalized scRNA-seq data. Gene Set Enrichment analysis (GSEA) v3 will be performed to evaluate the significance activation of the Hallmark and KEGG gene sets in MSigDb. This analysis will help us understand what specific pathways are activated in tumor cells and how the pathways are changing after treatment. Single cell trajectory analysis will be conducted with diffusion pseudotime method using Bioconductor package "destiny", which will capture the dynamic changes of tumor cells before and after treatment.

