10.0 STUDY CALENDAR

Table 10 describes required procedures. All procedures may increase in frequency if clinically indicated or oriented following toxicity. Adjustments to the treatment cycle due to a hold in study agent are detailed in [Section 5.2](#).

Table 10.0 Study Activity Calendar

	Screen -ing ^a	Cycle 1, 2, 3		Cycle 4+ Day 1 ^d	End of Treatment ^e				Active Follow-Up ^j
		Day 1 ^b	Day 14 ^c		Day 0 ^f	Days 1-11 ^g	Day 14 ^h	Day 30 ⁱ	
Informed Consent ^k	X ^s								
Inclusion/Exclusion Criteria ^l	X								
Registration ^m	X ⁿ								
Medical history ⁿ	X								
Physical exam	X	X		X				X	
Vital signs ^o	X	X		X				X	
Adverse events assessment ^p		X	X	X	X	X		X	
Concomitant meds review	X	X		X	X			X	
ECOG status (Appendix A) ^q	X	X		X				X	
Pregnancy test ^q	X								
TB antigen test ^r	X								
Hepatitis A, B, C testing	X ^s								
Skin photographs ^t	X	X		X	X			X	X
mSWAT ^u	X	X		X	X			X	X
Skin biopsy ^v		X ^w		X ^w				X ^w	
CBC with differential ^x	X	X	X	X				X	X
Chemistry panel ^y	X	X	X	X				X	X
Response assessment ^z		X		X	X			X	X
Teriflunomide clinical testing ^{aa}				X			X ^{dd}	X ^{dd}	
Leflunomide administration ^{bb}		Daily							
Cholestyramine ^g						X ^g			

- a. All screening procedures to be performed within 21 days of start of study agent except informed consent, acute hepatitis panel, skeletal survey which may occur within 30 days of start of treatment (footnote u) and except for registration which must occur within 7 days from start of treatment (footnote n).
- b. Day 1 assessments to be performed within 5 days (120 hours) prior to Day 1 drug (except footnote u for C1 only). Day 1 safety assessments must be resulted and reviewed prior to administration of agent for the cycle that is initiating. Screening assessments, if performed within this aforementioned time frame, may serve as C1D1 assessments. Note: items with footnote "aa" are not performed for C1D1; the windows for screening assessments still apply.
- c. Day 14 evaluations have +/- 3 day window.
- d. Day 1 assessments to be performed within 5 days (120 hours) prior to Day 1 drug. Day 1 safety assessments must be resulted and reviewed prior to administration of agent for the cycle that is initiating.
- e. Reasons to end study treatment include disease progression and unacceptable toxicity. See Section 5.8 for all criteria.

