- f. End of Treatment (EOT) Day 0 is defined as the day the determination to end treatment is made. EOT Day 0 assessments to be performed as soon as feasible, especially in the event of off treatment due to unacceptable toxicity and no later than 7 days after decision to end treatment; assessments performed after last dose of study agent(s) and within 7 days of the decision to end treatment may serve as EOT Day 0 assessments.
- g. EOT Day 1 is defined as the day cholestyramine administration begins; it will usually follow immediately after EOT Day 0, although it will not be deviation if this does not occur. If it does not follow immediately after EOT Day 0, the rest of calendar will follow per the actual EOT Day 1 (not EOT Day 0). Cholestyramine (8 grams three times daily for 11 days) will be administered according to [Section 5.5](#).
- h. EOT Day 14 assessments must occur after completion of cholestyramine, and may occur on Day 14 +/- 3 day window. If the cholestyramine administration period is extended beyond 11 consecutive days, the EOT Day 14 assessments may occur outside of this defined window.
- i. EOT Day 30 visit has a +/- 2 day window, however this window may be adjusted without deviation to ensure that it corresponds to the final teriflunomide clinical test (see footnote ee). All participants will be followed until resolution or stabilization of any serious adverse events occurring during treatment or starting within 30 days of last study drug administration or within the time to complete the EOT Day 30 assessments, which every occurs later.
- j. Active follow-up will occur for participants who have completed EOT procedures and yet to demonstrate disease progression. Disease response will be assessed every 3 months. Active follow-up will continue for 12 months or until disease progression, whichever is earlier.
- k. Informed consent process to be fully documented: e.g. prospective participant had sufficient time for deliberation, all questions were answered, treatment options provided by MD, full study reviewed including risks, and a copy of signed consent given to participant.
- l. Inclusion/exclusion criteria are detailed in [Section 3](#).
- m. See [Section 4.3](#) for slot reservation and registration process. Treatment must begin within 7 days of registration. Documentation providing Investigator's confirmation that all eligibility criteria are met must be available prior to registration.

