- n. Medical history to include review treatment history for CD30+LYPD medical history pertaining to eligibility, and demographic information.
- o. Vital signs: Weight, heart rate, blood pressure, respiration rate, temp. Height required only at baseline.

- p. Adverse event (AE) reporting begins for events that occur after start of study agent. AE recording and reporting will continue until the completion of the EOT Day 30 visit or until resolution or stabilization of any serious AE occurring before the completion the EOT Day 30 assessments, which every occurs later.
- q. Serum or urine pregnancy test for women of child bearing potential only.
- r. T-Spot or other TB antigen test.
- s. Consent, acute hepatitis panel, to be completed within 30 days prior to registration.
- t. Skin photographs: for subjects with skin lesions, up to five designated index lesions, representative of the subject's extent of disease, will be selected at baseline and measured and photographed using a digital camera. Photos should be taken against a blue backdrop. The photos will be taken on Day 1, prior to the first dose and then Cycle 2 Day 1 (-7 days) then every Cycle. In addition, half-body global photos (waist to feet, waist to top of head and sides) will also be obtained. Photos must be labeled with patient's protocol number and initials.
- u. Modified Severity Weighted Assessment Tool (mSWAT)[30] ([Appendix C](#))
- v. skin biopsies for research will not be taken at baseline if patients have a recent biopsy taken containing needed information.
- w. skin biopsies for research at baseline, at C2D1, C5D1, and EOT (if lesions are present), and at disease progression ([Section 9.2](#)).
- x. CBC with differential: erythrocytes (RBC), hemoglobin, hematocrit, platelets, total WBC plus absolute differential counts (neutrophils, lymphocytes, monocytes, eosinophils, basophils).
- y. Serum chemistry panel: Comprehensive metabolic panel (sodium, potassium, chloride, carbon dioxide, creatinine, urea nitrogen, calcium, glucose, albumin, total bilirubin, alkaline phosphatase, total protein, ALT/SGPT, AST/SGOT) LDH, magnesium, phosphorus, and uric acid.
- z. See [Section 11.2](#) for response assessment criteria.
- aa. Teriflunomide clinical blood assay to be ordered as "leflunomide metabolite" miscellaneous clinical test.

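### The baseline research biopsy is not tied to the washout of prior therapy, and Section 9.2.2, footnote v and Table 10 disagree on when it is taken

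*Combined protocol and SAP*

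**What the plan says.** **Timing of the baseline sample.** The protocol gives three answers.
- Section 9.2.2: "baseline samples may be collected anytime post-informed consent and prior to the Cycle 1 Day 1 dose".
- Table 10 marks the skin biopsy under Day 1 and not under Screening. Footnote b gives Day 1 assessments a window of 5 days before drug.
- Footnote v drops the baseline research biopsy when a recent one already holds the needed information. It does not define recent and does not mention prior therapy.

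Footnote w lists the biopsy time points and sends the reader back to Section 9.2.

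**Earliest consent.** Footnote a sets 21 days for screening procedures but excepts "informed consent, acute hepatitis panel, skeletal survey which may occur within 30 days of start of treatment". Footnote s has "Consent, acute hepatitis panel, to be completed within 30 days prior to registration", and footnote m adds "Treatment must begin within 7 days of registration".

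**Prior therapy.** Inclusion criterion 7 requires "At least 2 weeks from prior therapy to time of start of treatment", with an exception for prednisone or equivalent up to 10 mg/day. Exclusion criterion 1 bars "concurrent biological, chemotherapy, or radiation therapy during the study treatment period". Section 5.9.2 lists as prohibited "Exposure to any new immunosuppressive medication in the 4 weeks prior to enrollment".

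**Use of the sample.** Section 9.2.6 analyzes the baseline and start-of-Cycle-2 samples of each patient together, in part to learn "how the pathways are changing after treatment". Section 9.2.7 uses immunohistochemistry on all specimens to examine what leflunomide does to the tumor and its surroundings.

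**The concern.** Each rule on prior therapy is anchored to something other than the biopsy: the first dose (inclusion 7), the treatment period (exclusion 1), or newly started agents before enrollment (Section 5.9.2). A patient still on an earlier treatment at consent can be biopsied that day, stop later, complete the 2 weeks, and start leflunomide with every rule met. The baseline tissue then shows disease under one drug, and the Cycle 2 tissue shows disease off that drug and on leflunomide.

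The plan itself gives reason to expect withdrawal to matter. Everyone enrolled has had at least one earlier line of therapy. Section 2.1 says of phototherapy and methotrexate in lymphomatoid papulosis that the disease generally returns at its former level once they are stopped. A shift of that kind could be credited to leflunomide or could hide its effect, and it would vary between patients with the drug stopped and the biopsy date.

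At stake is the exploratory work meant to show how leflunomide acts and to guide later combinations (Section 2.4). A baseline sample cannot be retaken once leflunomide has started.

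**Working it through.** The plan states no figure on this point, so there is none to reproduce. The check is how many permitted biopsy days fall before prior therapy must have stopped.

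**Inputs**
- Washout before first dose: 14 days (inclusion 7).
- W, the earliest permitted biopsy in days before first dose: 5 (footnote b), 21 (footnote a, if the biopsy counts as a screening procedure), 30 (Section 9.2.2 with consent at the footnote a limit), or 30 + 7 = 37 (Section 9.2.2 with footnotes s and m).
- Cycle length: 28 days (Section 5.2).

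**Formulas**
- Permitted days before the latest required stop date: D = max(0, W − 14).
- Share of the window: D / W.
- Longest interval from baseline to Cycle 2 Day 1: 28 + W.

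| Governing window | W | D | D / W | 28 + W |
|---|---|---|---|---|
| Table 10 with footnote b | 5 | 0 | 0% | 33 |
| Footnote a, screening | 21 | 7 | 33% | 49 |
| 9.2.2, consent per footnote a | 30 | 16 | 53% | 58 |
| 9.2.2, consent per footnotes s and m | 37 | 23 | 62% | 65 |

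Footnote v sets no W, so no figure can be given for a substituted biopsy.

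Footnote b also allows the Cycle 2 assessments up to 5 days early. The interval under the calendar is therefore 28 − 5 = 23 to 28 + 5 = 33 days, against as much as 58 or 65 under Section 9.2.2.

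The zero in the first row means that no permitted day is on therapy. It does not mean that washout is complete: a patient who stops exactly 14 days before dosing and is biopsied 5 days before it has been off therapy for 14 − 5 = 9 days.

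**Can the analysis separate the two effects?** The study has one arm, so no concurrent group shows what withdrawal alone does. The linear models in Section 9.2.6 remove only UMI count and mitochondrial content. Neither represents the prior drug or the time since it stopped.

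**Illustration (assumed values, not from the documents).** Suppose leflunomide has no effect, k of 12 patients were biopsied on therapy, and stopping it shifts a gene by w log2 units. The mean spurious change is (k / 12) × w.
- k = 3, w = 0.5: 0.125
- k = 3, w = 1: 0.25
- k = 6, w = 1: 0.50
- k = 12, w = 1: 1.00
- k = 12, w = 1.58 (a threefold change): 1.58

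The result depends wholly on k and w, and the documents give neither.

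**The case against.** The strongest reply is that the calendar already solves the problem. Table 10 places the biopsy at Day 1, and footnote b puts it inside the washout. Even as a screening procedure it would fall under the 21-day limit, since biopsy is not among footnote a's exceptions. The 30- and 37-day windows need the Section 9.2.2 parenthesis to override both, and 37 also needs footnote s to prevail over footnote a. This stands as an argument for reporting a range. It does not remove the permission: footnote w refers to Section 9.2, where the explicit wording is the wider one. Footnote b's own exception cites footnote u, which now concerns mSWAT, so its scope is unclear.

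Second, the work is exploratory. The contrast in Section 12.4 is responders against non-responders, and the ex vivo exposure of pre-treatment specimens in Section 2.5 is not a baseline-to-Cycle-2 comparison. Natural disease variation already limits any before-and-after reading. All of this stands and sets the weight of the point.

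Third, a reader might infer from 53% or 62% that most baselines would be confounded. The documents do not support that. These are shares of calendar days with consent at its earliest. A sample is affected only if therapy was still running when it was taken, and the plan does not say how often that will happen. Prednisone that continues within the allowance adds no withdrawal effect. Footnote v applies only where the earlier tissue is adequate, which may limit its use.

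Fourth, much of the needed information is already gathered: collection date on the sample label (Section 9.2.4), treatment history (footnote n), and concomitant medication at screening. That stands, and makes the remedy cheaper.

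**Conclusion.** The point holds as a conflict in the text with a real but bounded consequence. Section 9.2.2 and footnote v allow a baseline research sample on prior therapy, and Table 10 with footnote b does not. Where it happens, the paired RNA and immunohistochemistry change cannot be attributed to leflunomide alone.

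The exposed part of the window runs from 0 to 23 days, according to which provision governs. The bias itself cannot be sized, because it needs the number of patients biopsied on therapy and the effect of stopping, and neither is given. With about 12 pairs, each affected baseline is 1/12, or about 8%, of the paired data.

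A reader might go further and conclude that the trial's efficacy findings are compromised. They are not: overall and complete response, duration of response and toxicity do not use the research biopsy. This is a low-cost improvement to an exploratory analysis and does not put the trial's main results in doubt.

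**What to change.** 1. Reword the parenthesis in Section 9.2.2 to match Table 10 and footnote b: a newly taken baseline research sample falls within 5 days before Cycle 1 Day 1 and after the inclusion 7 washout is complete. A patient who stops exactly 14 days before dosing can still meet both conditions with a pre-dose sample on Day 1.
2. Amend footnote v so that an earlier biopsy may still be used without a repeat procedure, but is flagged as such.
3. Record the last prior therapy and its stop date with each baseline sample, next to the collection date already on the label.
4. State in Sections 9.2.6 and 9.2.7 that the paired change analysis is reported with and without samples taken before the washout was complete.

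**Cost.** Wording changes and a small addition to the data collected, with no extra biopsy, visit or patient. The downside is less freedom in scheduling the baseline biopsy and fewer pairs in the sensitivity analysis, which starts from only about 12. The documents do not show that 14 days clears the effect of earlier drugs on expression. The change applies the plan's own washout to the biopsy and claims no more than that.
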